### 10.2.2 Sensitivity Analyses

The following sensitivity analyses will be conducted:

1. The mean, the median, and the 95% credibility intervals for  $\mu_d$ ,  $\Delta_d$ ,  $\exp(\xi_1)$ ,  $\exp(\xi_2)$ , and  $\exp(\xi_3)$ ; as well as the posterior probabilities,  $Pr(\Delta_d < -0.3)$ ,  $Pr(\text{dose } d \text{ is MED})$ , and  $Pr(\text{dose } d \text{ is ED}_{85})$ , will be presented for the longitudinal analysis used in the imputation of  $y_{4,i}$ .
2. The primary-analysis approach according to the planned treatment allocation will be carried out on the PP analysis set.
3. The primary-analysis approach according to the planned treatment allocation will be carried out on the ITT-RT analysis set, replacing  $\mu_d$  by  $\alpha_1$  in the conditional mean of missing  $y_{4,i}$  when imputing from the longitudinal model, that is, using a Missing Not At Random (MNAR) placebo model for the imputation of subjects who drop out.
4. The primary analysis according to the planned treatment allocation will be carried out on the ITT-RT analysis set using priors with twice as large scale parameters (standard deviations for normal distributions) than used for the primary analysis.
5. A Bayesian analysis will be performed for the observed value at Week 12 for completers, using a seed=10 000 and the same burn-in and thinning factor as specified for the longitudinal analysis, obtaining a final posterior sample size equal to the posterior sample size obtained in the primary analysis.

6. The primary-analysis approach but using the actual treatment allocation will be carried out on the Safety-RT analysis sets.
7. A mixed-effect model for repeated measurements (MMRM) analysis according to the planned treatment allocation will be performed on the ITT-RT analysis set using Markov chain Monte Carlo (MCMC) to impute intermediate missing 1000 times with seed=742738, and an MNAR placebo-based pattern mixture model (see [Ratitch 2011](#)) to impute after drop out for each of the 1000 imputed data set with monotone missing pattern, using the seeds 841621, 745274, 830367, and 995004 for the imputation of missing at Week 1, Week 4, Week 8, and Week 12, respectively. The systematic effects will comprise visit number and treatment-by-visit as categorical variables, and baseline-RT number of nocturnal voids minus 2 as a linear covariate interacting with visit number. An unstructured covariance matrix will be used. The estimated contrasts to placebo at Week 12 will be presented with 95% confidence intervals. Based on the same sets of imputed data, the log-linear trend across active doses (replacing the categorical treatment variable with an indicator variable for treatment with Placebo and a linear variable,  $\log_2(d/0.5)$ ) and the linear trend across all doses (replacing the categorical treatment variable with the linear variable,  $d$ ) will be estimated with 95% confidence limits.

### **10.2.3 Descriptive analysis**

The mean aggregated average and mean aggregated average change from baseline for each dose at each visit will be tabulated together with 95% confidence intervals as a part of the explorative benchmarking analyses described in Section [10.5](#).

## **10.3 Secondary Efficacy and Exploratory Analyses**

### **10.3.1 General Considerations**

The following main categories of inferential analyses will be performed for the secondary efficacy endpoints:

- Bayesian estimation of the sigmoidal dose-response curve will be used for aggregated averages and for the aggregated responder variable, 50% reduction from baseline-RT in number of nocturnal voids, defined as the aggregated average change from baseline being less or equal to 50% of the baseline-RT number of nocturnal voids. For details, see Section [10.3.3](#).
- MMRM will be used to evaluate treatment effects on cross-sectional change from baseline for quantitative variables. For details, see Section [10.3.4](#).
- General Estimating Equations with the logit as link function will be used for cross-sectional binary responder variables. For details, see Section [10.3.5](#).
- Analysis of covariance (ANCOVA) will be used for the single-time-point quantitative variables: percentage of nights during treatment period with at most 1 nocturnal void and with a complete response, respectively, and change from baseline in copeptin levels. For details, see Section [10.3.6](#).

- Correlation between endpoints will be reported using Pearson correlation coefficients and linear regression coefficients, regressing total sleep on FUSP and NPi on copeptin.

**Table 5** presents the planned analyses for all endpoints. All analyses will be performed on the observed data in the ITT-RT analysis set unless otherwise specified. Visit windows for each endpoint will be as described in Section 3.1.5.

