4.1.1 Inclusion Criteria

Each subject must meet the following inclusion criteria between Visit 1 (screening) through Visit 4 (randomisation):

1. Written informed consent prior to performance of any trial-related activity
2. Adults ≥ 18 years of age (at the time of written consent)
3. Female subjects of child-bearing potential must be willing and able to use adequate contraception throughout the trial. Documentation of an acceptable effective method of contraception must be available. All pre- and perimenopausal subjects have to perform pregnancy tests. Amenorrhea of more than 12 months duration based on the reported date of the last menstrual period is sufficient documentation of post-menopausal status and does not require a pregnancy test
4. Medical history of, or subject reported nocturia symptoms during the 6 months prior to Visit 1
5. ≥ 2 nocturnal voids (an average over 3 days) as documented in the 3-day e-Diary prior to Visit 2
6. The largest single voided volume must be ≥ 200 mL (at least 1 void ≥ 200 mL) as documented in the 3-day e-Diary prior to Visit 2
7. Nocturnal polyuria, defined as $NP_i > 33\%$, a ratio of NUV in excess of 33% of total daily (24-hour) urine volume as documented in the 3-day e-Diary prior to Visit 2
8. ^b
9. $\geq 20\%$ decrease in the nocturnal diuresis rate (mL/min) (that was recorded at Visit 2) as documented in the 3-day e-Diary prior to Visit 3
10. Additionally to be randomised into the trial at Visit 4 subjects must have ≥ 2 nocturnal voids (an average over 3 days) as documented in the 3-day e-Diary prior to Visit 4

^b Original inclusion criterion omitted as per Clinical Trial Protocol Amendment 02 (applicable for all trial sites).

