6.3 Visit 2 Active Run-in Period

All assessments and procedures to be performed at Visit 2 are listed below.

- The subject will complete the questionnaire (ISI), in the e-Diary (Section 7.1.1.3.2), at the trial site before any consultation with the trial site personnel takes place.
- Inclusion and exclusion criteria will be evaluated.
- Body weight will be measured.
- Vital signs (blood pressure and heart rate) will be measured.
- The subject will be interviewed about any changes in concomitant medication and about any adverse events since the last visit.
- Blood samples will be drawn for assessment of copeptin.
- The subject will be reminded about lifestyle changes (Section 4.3.3).
- Instructions for start and use of IMP will be given.
- IMP will be dispensed to eligible subjects for the 1-week active run-in (Table 5-1).

Prior to Visit 3 the subject will be reminded to complete the e-Diary (Section 7.1.1) for 3 consecutive days prior to the visit. The e-Diary will be reviewed for completeness (via the web-portal) by the trial site personnel.

Four days after the planned start of IMP treatment the subject will be telephoned to follow-up on safety.

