7.1.3.3 Copeptin

Blood samples for exploratory analysis of copeptin levels in plasma will be collected at Visit 2, Visit 4 and Visit 8. The biomarker copeptin can be easily tested for, and is therefore used as an AVP surrogate to potentially identify low nocturnal vasopressin levels in plasma. In patients with NP, an inverse circadian rhythm of vasopressin is suspected, resulting in low nocturnal concentrations, which may be the root cause of NP. Copeptin may be a useful biomarker to diagnose NP due to low levels of endogenous AVP, thereby identifying the ideal candidate for antidiuretic therapy (Brunell, 2016) and consequently treatment with FE 201836.

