### **Exploratory Endpoints**

- Responder rates defined as 33%, 60%, 70%, 80%, 90% and 100% reduction from baseline in number of nocturnal voids at Weeks 1, 4, 8 and 12.
- Responder rates defined as 1, 2, and 3 voids reduction from baseline in number of nocturnal voids at Weeks 1, 4, 8 and 12.
- The correlation of copeptin levels to NPi at Visit 2.
- Change from baseline in copeptin levels at Week 12.
- Change from baseline in total sleep time per night at Weeks 1, 4, 8 and 12 and during 12 weeks of treatment.
- Correlation between change from baseline in total sleep time and FUSP at Weeks 1, 4, 8 and 12.
- Change from baseline in NPi at Week 1 and Week 12.

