### 5.2 Randomized-Treatment-Period Analysis Sets

#### 5.2.1 Intention-To-Treat Analysis Set for the Randomized-Treatment Period (ITT-RT)

The Intention-to-Treat analysis set for the randomized-treatment period (ITT-RT) comprises all subjects randomized at Visit 4.

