## 10 Efficacy

### 10.1 General Considerations

For endpoints obtained from the Voiding Diary prior to a visit, the average of the endpoint across the 3 days will be interpreted as the cross-sectional observation of the endpoint in question at the specific visit, with the exception of the two endpoints, “Percentage of nights during the treatment period with at most one nocturnal void” and “Percentage of nights during the treatment period with complete response, i.e., with no nocturnal voids”.

If the baseline number of nocturnal voids is missing for a reason that can be considered to be missing completely at random (e.g., missing due to technical problems of the eDiary), the subject will not be included in any analyses that involve baseline measurements of nocturnal voids or other variables derived using baseline measurements of nocturnal voids.

The Bayesian dose-response analyses are conducted on aggregated averages, that is, outcomes averaged across preceding post-randomization visits. The posterior mean, median, and 95% credibility interval (2.5 and 97.5 percentiles of the posterior distribution) of quantities of interest as well as posterior probabilities of interest will be reported.

Frequentist inferences will rely on the appropriate choice of model and report p-values corresponding to the statistical test of the hypothesis of “no difference / no association” against the alternative of “any difference / any (linear) association”. The level of significance is set at 5% (two-sided).

Treatment comparison refers to the pair-wise comparison between each of the different doses of active treatment with FE 201836 and placebo. There are no planned adjustments for multiplicity when pair-wise testing the active treatment with different doses of FE 201836 versus placebo. Desmopressin is included as a benchmark treatment only. None of the primary, secondary or explorative analyses will include data from subjects treated with desmopressin. Explorative benchmarking analyses are further described in Section 10.5.

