Lowest observed change from baseline-RT in Serum Sodium				Alternative safety indicator for therapeutic window	
Incidence and severity of Adverse Events	Section 11.3.1				
Adverse Event of Special Interest: Hyponatraemia Episodes	Section 11.2.1				
Clinically significant changes in laboratory values and vital signs	Sections 11.3.2 and 11.3.3				

a Endpoint assessed at Weeks 1, 4, 8 and 12.

b Endpoints are derived using all diary data collected during the treatment period.

c Endpoint assessed at Weeks 1 and 12.

d Correlation between changes in FUSP and total sleep time at Weeks 1, 4, 8 and 12.

e This questionnaire is retrospective and raw scores will be used in the analysis (not changes from baseline) and the ANCOVA model will not be adjusted for baseline value.

f Endpoint assessed at Weeks 4, 8 and 12.

g Correlation with NPI at Visit 2.

h Endpoint assessed at Week 12.

Illustration of the therapeutic window is described separately in Section 10.4 and safety related endpoints are further described in Section 11.

Explorative analyses by sex are planned for all endpoints, including correlation analyses. For these the following are noted:

- Estimates of the sex-specific dose-response for the aggregated averages after 12 weeks of treatment will follow the Bayesian analysis described in Sections 10.2.1 and 10.3.3 by conducting a separate analysis for each sex. Possible differences between the sex-specific models will be investigated.
- The regression models will be supplemented with an analysis considering sex as well as all interactions between sex and the effects specified in the all-subjects analysis, including any interaction terms specified in the all-subject analysis. Possible differences between the treatment effects for men and women will be evaluated by the treatment-by-visit-by-sex (treatment-by-sex for single-visit outcomes) interaction term with the effect of treatment-by-visit (treatment for single-visit outcomes) included in the model.

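### The Visit 2 copeptin–NPi correlation is limited by default to randomised subjects not on desmopressin, although both values precede any trial drug and ITT-ENR is available.

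*SAP*

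**What the plan says.** The endpoint is listed in SAP 2.2 as "The correlation of copeptin levels to NPi at Visit 2". It has a row in SAP Table 5, marked explorative, and footnote g adds only "Correlation with NPI at Visit 2". No analysis set is named there.

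Two general rules therefore decide who enters:

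- SAP 10.3.1 gives the default: "All analyses will be performed on the observed data in the ITT-RT analysis set unless otherwise specified". By SAP 5.2.1, ITT-RT "comprises all subjects randomized at Visit 4".
- SAP 10.1 adds: "None of the primary, secondary or explorative analyses will include data from subjects treated with desmopressin". SAP 10.5 makes room for desmopressin in the benchmarking summaries, but copeptin is not among them.

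The measurements come earlier. For Visit 2, Protocol 6.3 states: "Blood samples will be drawn for assessment of copeptin". Run-in IMP is dispensed at that same visit and taken at bedtime (Protocol 5.1). NPi comes from the 3-day diary completed before Visit 2. Randomisation then requires, among other things, a 20% or greater "decrease in the nocturnal diuresis rate (mL/min) (that was recorded at Visit 2) as documented in the 3-day e-Diary prior to Visit 3" (Protocol 4.1.1, criterion 9).

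The SAP already has a wider set. ITT-ENR (SAP 5.1.1) contains everyone found eligible at Visit 2, and SAP 6.1.5 uses it to summarise Visit 2 copeptin descriptively.

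**The concern.** A correlation between two pre-dose measurements has no need of post-randomisation information, yet the plan admits subjects according to what happens to them afterwards. Two separate losses follow.

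- **Desmopressin arm.** Allocation at Visit 4 cannot alter a blood sample or diary taken at Visit 2. Excluding these subjects discards valid pairs.
- **Entrants not randomised.** These are run-in non-responders, subjects excluded on serum sodium at Visit 3, and subjects with fewer than 2 voids before Visit 4. Leaving out non-responders selects on response to a V2 agonist. Protocol 7.1.3.3 hopes copeptin may mark low endogenous AVP, "thereby identifying the ideal candidate for antidiuretic therapy". If copeptin or NPi is related to drug response, selecting on response can change their correlation with each other.

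At stake is the precision of one exploratory coefficient and the population it describes.

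**Working it through.** **1. Subjects lost through the desmopressin rule**

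Inputs: 125 subjects allocated 2:2:1 in stage 1, 2:7:1 thereafter, maximum 300 randomised (Protocol 3.3; SAP 3.1.1 and 3.1.2).

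- Stage 1: 125 × 1/5 = 25. This matches the 25 stated in Protocol Appendix 2, section 3.1.
- Stage 2 at full accrual: (300 − 125) × 1/10 = 17.5.
- Total: 42.5 of 300 = 14.2%, leaving about 257.

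In general the number is 25 + (N − 125)/10:

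| N randomised | Desmopressin | Share |
|---|---|---|
| 125 (stop at first interim) | 25 | 20.0% |
| 200 (null-scenario average) | 32.5 | 16.3% |
| 277 (scenario I average) | 40.2 | 14.5% |
| 300 | 42.5 | 14.2% |

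**2. What that costs in precision**

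Fisher z, SE = 1/√(n − 3). At r = 0 the 95% half-width is tanh(1.96/√(n − 3)).

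- n = 257: tanh(1.96/√254) = 0.122.
- n = 300: tanh(1.96/√297) = 0.113.

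At r = −0.2 the half-widths are 0.118 and 0.109. Because arm is assigned at random after Visit 2, this exclusion introduces no bias.

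**3. Subjects lost because they were not randomised**

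The documents give no proportion of ITT-ENR expected to be randomised, so a range is assumed, with 300 randomised:

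| Assumed share of ITT-ENR randomised | ITT-ENR n | Share used under current rules (257.5/n) | Half-width at r = 0 in ITT-ENR |
|---|---|---|---|
| 90% | 333 | 77% | 0.107 |
| 70% | 429 | 60% | 0.095 |
| 50% | 600 | 43% | 0.080 |

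**4. Whether selection on response moves the correlation**

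Take a trivariate normal model with true copeptin–NPi correlation r, and correlations a and b of copeptin and NPi with run-in response. Select the top fraction p on response. With c the cut-point, λ = φ(c)/p and k = λ(λ − c), the correlation after selection is

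r′ = (r − kab) / √[(1 − ka²)(1 − kb²)].

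All of r, a, b and p are assumptions. With r = −0.30:

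- p = 0.4: c = 0.253, λ = 0.966, k = 0.688.
- p = 0.8: c = −0.842, λ = 0.350, k = 0.417.

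| a and b | p = 0.8 | p = 0.4 |
|---|---|---|
| opposite signs, size 0.1 | −0.30 | −0.30 |
| opposite signs, size 0.3 | −0.27 | −0.25 |
| opposite signs, size 0.5 | −0.22 | −0.15 |
| same sign, size 0.3 | −0.35 | −0.39 |
| same sign, size 0.5 | −0.45 | −0.57 |

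If only copeptin is related to response (a = −0.3 to −0.5, b = 0), the result is −0.31 to −0.33. Selection can therefore weaken the coefficient, strengthen it or leave it almost unchanged.

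**The case against.** The strongest reply is that ITT-RT is not an arbitrary choice. The protocol enriches deliberately for V2-responsive subjects (Protocol 3.5.1), and a correlation in that population is valid for that population. The endpoint is exploratory, and the Visit 2 data remain available for a later ITT-ENR analysis. All of this stands, and it limits the importance of the point. It does not explain why a pre-dose correlation should depend on later events when ITT-ENR already carries the descriptive copeptin summary.

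Four stronger readings are tempting, and the documents do not support them.

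- *Selection pulls the correlation towards zero.* That requires copeptin and NPi to relate to response with opposite signs and appreciable size. Low copeptin and high NPi both favouring response would be plausible, but no figure is given, and same-sign relations push the other way.
- *The biomarker objective cannot be answered from responders.* The stated objective concerns low nocturnal vasopressin, and the endpoints are the Visit 2 correlation and the Week 12 change. Predicting run-in response is not a listed objective or endpoint, so the absence of a responder versus non-responder or ROC analysis is not a defect.
- *The desmopressin exclusion has no reason.* A general one is given in SAP 10.1 and Protocol 9.7.1: desmopressin is a benchmark only. The fair criticism is that this concerns treatment comparisons and does not fit a Visit 2 sample.
- *No non-responder can be in the analysis.* One randomised in error stays in ITT-RT; that deviation removes the subject only from the PP set.

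**Conclusion.** The point holds, at low consequence. Read literally, the two general rules confine a correlation of two pre-dose values to randomised subjects not on desmopressin, with no exception and no reason specific to this analysis. SAP section 14 calls the use of ITT-RT with observed data a clarification and says nothing about pre-treatment measurements.

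The desmopressin part is firm in size: about 42 of 300 (14%) at full accrual, up to 20% with a stop at the first interim. Its effect is confined to precision and is small. The loss of non-randomised entrants is probably the more important part, because it conditions on drug response, but its size rests on an unstated pass rate and its effect on the coefficient on unstated correlations. Possible distortion is established; direction and amount are not.

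The coefficient feeds no success, futility, MED, ED85, allocation or safety decision.

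**What to change.** In SAP 10.3.1 and Table 5 footnote g, state that the Visit 2 copeptin–NPi correlation and the regression of NPi on copeptin use all ITT-ENR subjects with both values, regardless of later randomisation or arm. Word this as an explicit exception to the desmopressin rule in SAP 10.1, and apply it to the planned by-sex versions. Keep the ITT-RT version as a sensitivity analysis.

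Add a note that ITT-ENR is limited by eligibility to NPi above 33% and at least 2 voids. One of the two correlated variables therefore remains truncated, and the change does not remove all range restriction.

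The cost is a few lines of SAP text and a second run of the same analysis. No new sample, visit or diary entry is needed. A comparison of Visit 2 copeptin between run-in responders and non-responders is optional and not needed to correct the planned analysis. If added, it should be labelled exploratory: the run-in is uncontrolled and response is judged from two 3-day diaries, so it mixes drug effect with diary noise and regression to the mean.

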**Table 5 Analysis of Endpoints**

Endpoint	Analysis category				
	Bayesian Estimation of Dose-response Curve for Aggregated Averages	MMRM	Repeated logistic regression (Generalized Estimating Equation [GEE])	ANCOVA	Correlation Analysis
Efficacy Endpoints					
Aggregated average change from baseline during the 12 weeks randomized-treatment period for number of nocturnal voids	Primary	Sensitivity, Therapeutic Window			
Change from baseline in number of nocturnal voids at the visit a		Secondary			
Rate of response defined as 50% reduction in nocturnal voids from baseline based on aggregated average change from baseline	Secondary		Secondary		
Rate of response defined as 50% reduction in nocturnal voids from baseline a			Secondary		
Rate of response defined as 33%, 60%, 70%, 80%, 90% and 100% reduction from baseline in number of nocturnal voids a			Explorative		
Rate of response defined as 1, 2, and 3 voids reduction from baseline in number of nocturnal voids a			Explorative		
Percentage of nights during treatment period with at most one nocturnal void b				Secondary	
Percentage of nights during treatment period with complete response b				Secondary	
Change from baseline in NUV c	Secondary	Secondary			
Change from baseline in FUSP a	Secondary	Secondary			Explorative d
Change from baseline in total sleep time per night a		Explorative			
Change from baseline in nocturnal diuresis rate (hourly) c		Secondary			
Change from baseline in NPi c		Explorative			
Change from baseline in NI Diary Total Score a	Secondary	Secondary			
Change from baseline in NI Diary Overall Impact Score a	Secondary	Secondary			

Endpoint	Analysis category				
	Bayesian Estimation of Dose-response Curve for Aggregated Averages	MMRM	Repeated logistic regression (Generalized Estimating Equation [GEE])	ANCOVA	Correlation Analysis
PGI-I urinary symptoms score a, e		Secondary			
Change from baseline in PGI-S score a		Secondary			
Change from baseline in Bother as measured by the Hsu 5-point Likert Bother Scale a		Secondary			
Change from baseline in ISI f		Secondary			
Copeptin levels at Visit 2 g					Explorative
Change from baseline in copeptin levels h					Explorative
Safety Endpoints					
Change from baseline in mean 24-hour urine volume c		Safety			
Lowest observed change from baseline-RT in Serum Sodium				Alternative safety indicator for therapeutic window	
Incidence and severity of Adverse Events	Section 11.3.1				
Adverse Event of Special Interest: Hyponatraemia Episodes	Section 11.2.1				
Clinically significant changes in laboratory values and vital signs	Sections 11.3.2 and 11.3.3				

a Endpoint assessed at Weeks 1, 4, 8 and 12.

b Endpoints are derived using all diary data collected during the treatment period.

c Endpoint assessed at Weeks 1 and 12.

d Correlation between changes in FUSP and total sleep time at Weeks 1, 4, 8 and 12.

e This questionnaire is retrospective and raw scores will be used in the analysis (not changes from baseline) and the ANCOVA model will not be adjusted for baseline value.

f Endpoint assessed at Weeks 4, 8 and 12.

g Correlation with NPI at Visit 2.

h Endpoint assessed at Week 12.

Illustration of the therapeutic window is described separately in Section 10.4 and safety related endpoints are further described in Section 11.

Explorative analyses by sex are planned for all endpoints, including correlation analyses. For these the following are noted:

- Estimates of the sex-specific dose-response for the aggregated averages after 12 weeks of treatment will follow the Bayesian analysis described in Sections 10.2.1 and 10.3.3 by conducting a separate analysis for each sex. Possible differences between the sex-specific models will be investigated.
- The regression models will be supplemented with an analysis considering sex as well as all interactions between sex and the effects specified in the all-subjects analysis, including any interaction terms specified in the all-subject analysis. Possible differences between the treatment effects for men and women will be evaluated by the treatment-by-visit-by-sex (treatment-by-sex for single-visit outcomes) interaction term with the effect of treatment-by-visit (treatment for single-visit outcomes) included in the model.

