- Estimates of the gender specific dose-response during 12 weeks of treatment will follow the analysis described in Section 9.7.2.3 by conducting separate analysis for each gender. Possible differences between the gender specific models will be investigated.
- Regression models will include gender and gender-by-treatment as factors. (Possible differences between the treatment effects on gender will be evaluated by the interaction term gender-by-treatment.)

Correlation analyses will be done separately for each gender.

Table 9-4 Analysis of Endpoints

	Analysis category				
	Bayesian Estimation of Dose-response Curve	Repeated measures ANCOVA	Correlation Analysis	Repeated logistic regression (Generalized Estimating Equation [GEE])	ANCOVA
Efficacy Endpoint					
Change from baseline in number of nocturnal voids ^a	Primary	Secondary ^c			
Responder rate defined as 50% reduction in nocturnal voids from baseline ^a	Secondary			Secondary	
Change from baseline in NI Diary Total Score ^a	Secondary	Secondary			
Percentage of nights during treatment period with at most one nocturnal void ¹					Secondary
Percentage of nights during treatment period with complete response ¹					Secondary
Change from baseline in NI Diary Overall Impact Score ^a	Secondary	Secondary			
PGI-I urinary symptoms score ^{a,b}		Secondary			
Change from baseline in PGI-S score ^a		Secondary			
Change from baseline in Bother as measured by the Hsu 5-point Likert Bother Scale ^a		Secondary			
Change from baseline in ISI ^f		Secondary			
Change from baseline in FUSP ^a	Secondary	Secondary	Explorative ^h		
Change from baseline in nocturnal diuresis rate (hourly) ^c		Secondary			
Change from baseline in NUV ^c	Secondary	Secondary			
Responder rates defined as 33%, 60%, 70%, 80%, 90% and 100% reduction from baseline in number of nocturnal voids ^a				Explorative	
Responder rates defined as 1, 2, and 3 voids reduction from baseline in number of nocturnal voids ^a				Explorative	
Copeptin levels at Visit 2			Explorative ^g		
Change from baseline in copeptin levels ^d					Explorative
Change from baseline in total sleep time per night ^a		Explorative			
Change from baseline in NPi ^c		Explorative			
Safety Endpoints					
Change from baseline in mean 24-hour urine volume ^c		Safety			
Incidence and severity of Adverse Events	Section 9.10.2				
Adverse Event of Special Interest: Hyponatraemia Episodes	Section 9.10.3				

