#### **10.3.4 Treatment effects on cross-sectional change from baseline for quantitative variables and PGI-I**

Treatment effects on cross-sectional change from baseline for quantitative variables will be analysed using SAS PROC MIXED assuming a MMRM (a non-parametric dose-response curve is assumed). The systematic effects will comprise visit number and treatment-by-visit as categorical variables, and the baseline-RT value as a linear covariate interacting with visit number. An unstructured covariance matrix will be used if technically possible, alternatively a Toeplitz, a compound-symmetry, or if necessary, an independent covariance matrix will be used. The treatment contrasts (with associated 95% confidence intervals without multiplicity adjustment) versus placebo will be tabulated and graphically illustrated. The analyses will be applied to the observed data on the ITT-RT analysis set.

The same approach will be applied to the aggregated average change from baseline in number of nocturnal voids.

For PGI-I there is no baseline so the systematic effects will comprise only visit number and treatment-by-visit as categorical variables.

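### For repeated outcomes the SAP judges sex differences in drug effect only by a treatment-by-visit-by-sex term (24 df at four visits); one pre-specified visit-averaged dose-by-sex contrast with its interval would be a cheap improvement

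*SAP*

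**What the plan says.** SAP 10.3.1 labels the analyses by sex explorative and describes two routes.

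- **Bayesian route.** The dose-response analysis of the aggregated averages is run separately in each sex. Differences between the two fits are to be investigated, with no quantity or rule given.
- **Regression route.** The models are supplemented by "an analysis considering sex as well as all interactions between sex and the effects specified in the all-subjects analysis". The SAP then states: "Possible differences between the treatment effects for men and women will be evaluated by the treatment-by-visit-by-sex (treatment-by-sex for single-visit outcomes) interaction term", with treatment-by-visit kept in the model.

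The base model for quantitative outcomes is in SAP 10.3.4: "The systematic effects will comprise visit number and treatment-by-visit as categorical variables", plus baseline interacting with visit. There is no separate treatment main effect. For nocturnal voids and most other repeated outcomes the Table 5 note reads "Endpoint assessed at Weeks 1, 4, 8 and 12".

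Protocol 9.7.3 had named a different term: "Possible differences between the treatment effects on gender will be evaluated by the interaction term gender-by-treatment". SAP section 14 discloses that sex interactions were added to every model effect. Its reason is to keep the interaction evaluation consistent with the separate-sex analyses. It refers there to evaluation overall or by visit as appropriate, but 10.3.1 gives no overall version for repeated outcomes.

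**The concern.** The natural first question is whether the drug effect, over the treatment period, differs between men and women. The specified term asks something broader: whether any dose differs by sex at any visit, including differences in time pattern. A sex difference that is steady over visits and graded or constant over doses is diluted across many degrees of freedom. Several of these belong to dose groups that SAP section 14 expects to hold 20 subjects or fewer, so about 10 per sex.

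Sex matters in this programme. The benchmark drug is dosed by sex, and SAP 10.4 plans sex-specific therapeutic windows, on which section 13 rests the risk-benefit assessment. A non-significant result from a test with little chance of detecting a difference could be taken as reassurance, and the plan does not warn against that.

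**Working it through.** **Degrees of freedom.** SAP 10.1 excludes desmopressin, leaving 7 groups. With treatment-by-visit but no treatment main effect in the model, the three-way term absorbs treatment-by-sex. Its df are (7 − 1) × visits: 24 for four visits if all six doses are populated, 18 for ISI (three visits), 12 for two-visit outcomes. Single-visit outcomes have 6.

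**Nearest stated figure.** Neither document states power for a sex comparison. As a check on the SD, Scenario III implies an effect at 500 µg of 0.5 × 5⁴/(5⁴ + 2⁴) = 0.4875. With 85 placebo and an assumed 80 subjects at 500 µg, SE = 0.95 × √(1/85 + 1/80) = 0.148, and power is about 91% against the stated 90.4%. The 500 µg arm size is not fixed in the documents, so this approximates the simulated figure and does not reproduce it.

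**Inputs from the documents**
- Stage 1 (Protocol Appendix 2, 3.1): 50 placebo and 50 at 500 µg. Stage 2: 175 subjects at 2:7:1, about 35 placebo and 122 FE 201836. Total analysed: 85 + 172 = 257.
- SD 0.95 for the final endpoint (Appendix 2, 4.1.1), which Appendix 2, 1.2 defines as the average over four visits.
- About 50% of each sex (Protocol 4.1); dropout 15% (Protocol 9.1); 5% two-sided (SAP 10.1).

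**Assumptions**
- A sex difference in effect of 0.5 voids, constant over visits.
- Two dose splits (placebo, then 50–500 µg): 85/12/12/14/24/30/80 and 85/20/20/20/20/20/72.
- Compound symmetry over visits, known variance, and loss of 0 or 15% as a plain reduction in sample size.

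**Formulas.** Let δ_d be the sex difference at dose d and w_d = n_d/4 (equal sexes). The omnibus noncentrality is λ = Σ w_d(δ_d − δ̄)²/0.95², with δ̄ the weighted mean. Under compound symmetry and a visit-constant difference, λ is the same for the 24-df test and the visit-averaged 6-df test, so only the df differ. For a 1-df contrast with coding x, λ = [Σ w_d(δ_d − δ̄)(x_d − x̄)]²/[Σ w_d(x_d − x̄)² × 0.95²]. Power is the noncentral chi-square tail.

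**Worked case.** Difference of 0.5 at every dose, no loss: λ = 0.25 × (85 × 172/257)/4/0.9025 = 3.94. Power is 14.4% at 24 df, 26.6% at 6 df, and 51.0% for a pooled-drug-by-sex contrast. The linear-dose contrast has λ = 2.00–2.42 and power 29–34%.

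**Results (range over both splits and 0–15% loss)**

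| Shape of the 0.5-void difference | 24 df | 6 df | linear dose by sex | pooled drug by sex |
|---|---|---|---|---|
| Equal at all doses | 12.7–14.4% | 22.8–26.6% | 25.6–34.3% | 44.8–51.0% |
| Linear in dose, 0.5 at 500 µg | 10.6–12.2% | 18.1–21.6% | 36.5–42.9% | 21.0–28.6% |
| Scenario III shape, 0.5 at 500 µg | 12.0–13.8% | 21.3–25.3% | 40.6–47.1% | 22.0–32.1% |
| At 500 µg only | 11.8–14.0% | 20.9–25.8% | 33.0–37.9% | 11.9–15.2% |

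**Precision of the proposed estimate.** The SE of the linear-dose sex difference at 500 µg is 5 × 0.95/√[Σ w_d(x_d − x̄)²] = 0.28–0.31 voids. The 95% interval is therefore about ±0.55 to ±0.61.

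**The case against.** The strongest reply is that this is a disclosed, exploratory analysis with no promised power and no decision attached, and that any sex interaction is hard to detect with about 257 subjects in seven arms. All of that stands. The protocol's own 6-df term would reach only 18–27%, and the proposed contrast would still usually miss a 0.5-void difference. Linear coding also enters the SAP only as a supplement in case the sigmoidal fit has difficulties, so it is one reasonable choice among several. An omnibus test does cover patterns that a single contrast misses.

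Two stronger readings are tempting, but the documents do not support them.

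- A reader might infer that the trial will report a single MED and a single ED85 for both sexes. SAP 10.3.1 plans the Bayesian analysis separately by sex, following 10.2.1, which tabulates the MED and ED85 probabilities.
- A reader might infer a much larger power gap, with 1-df contrasts reaching 44–71%. That needs SD 0.95 at each visit, whereas the documents give it for the four-visit average. It also ignores dropout, and its top end comes from a pooled-drug contrast chosen to fit a difference equal at all doses. The table shows that contrast doing poorly when the difference is graded with dose.

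What the reply does not supply is a visit-averaged test or estimate of the sex difference for repeated outcomes. The section 14 rationale concerns model consistency, and the Bayesian curves come with no comparison quantity.

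**Conclusion.** The point holds as a modest improvement to an exploratory analysis. The SAP's only specified sex-difference test for repeated outcomes spreads a steady difference over up to 24 df. Under the stated assumptions that gives about 11–14% power. The protocol-type 6-df test gains about 8–12 points over this, and the linear-dose contrast about 13–33 points. The linear contrast is weakest, at 26–34%, when the difference is equal at all doses, where a pooled-drug contrast has 45–51%.

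The figures depend on an assumed 0.5-void difference, on dose splits that the adaptive allocation will determine, and on a difference constant over visits. The 24-df count does not apply to ISI, two-visit or single-visit outcomes. The low power is not mainly the SAP's wording: the sample is small for any interaction, so an estimate with its interval is worth more than a p-value from either test.

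**What to change.** In SAP 10.3.1, for repeated outcomes:

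1. Pre-specify a visit-averaged linear-dose-by-sex contrast. The dose coding *d* (units of 100 µg) is already in sensitivity analysis 7, which plans "the linear trend across all doses (replacing the categorical treatment variable with the linear variable" *d*).
2. Report the estimated sex difference in effect at 500 µg versus placebo with its 95% CI.
3. Keep the treatment-by-visit-by-sex term as a supplementary omnibus check.
4. State that a non-significant interaction is not evidence of equal effect in men and women.

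The cost is one extra contrast in models already planned and one SAP paragraph. The contrast loses power when the sex difference is not graded with dose, which is why the omnibus term is kept. No version of the test becomes adequately powered.
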